Weill Cornell Medical College

CLINICAL STUDY PROTOCOL

TITLE: Phase II Clinical Study of the Clinical Efficacy and Safety of Tosedostat in Patients with Myelodysplastic Syndromes (MDS) after Failure of Hypomethylating Agent-based Therapy

STUDY NUMBER: WCMC IST-CTI-MDS

INVESTIGATIONAL MEDICINAL PRODUCT: Tosedostat

IND No. 125244

INDICATION: High or Very High Risk Myelodysplastic Syndrome (MDS)

PRINCIPAL INVESTIGATOR:
[name]
Director of the Leukemia Program
Weill Medical College of Cornell University and NewYork-Presbyterian Hospital
[name]
[name]
[name]
[contact]
[contact]

CO-INVESTIGATORS:
[name]
[name], PhD
[name]
[name]
[name], MPH
[name]
[name], NP
[name], PA
[name]
[name], NP

STATISTICIAN [name] (Statistics consultant)

PROTOCOL VERSION AND DATE: Version 1.2 dated 06 October 2016

CROSS REFERENCE CTI BioPharma Corp – IND No. 75,503: Tosedostat (CHR-2797)

PROTOCOL SYNOPSIS

Purpose of the Study	Study WCMC IST-CTI-MDS evaluates the safety and tolerability of tosedostat in adult patients with pathologically confirmed myelodysplastic syndromes (MDS) after failure of hypomethylating agent-based therapy.
Primary Objectives	The primary objective the study is to evaluate the safety and efficacy of tosedostat patients with myelodysplastic syndrome who have relapsed after or are refractory or intolerant to azacitidine or decitabine. The primary endpoint is overall survival.
Secondary Objectives	
The following secondary endpoints will be evaluated in high and very high risk MDS patients:
 
 • Hematological improvements (erythroid response [ER], platelet response [PLR] and neutrophil response [NR]) according to 2006 IWG criteria (Appendix 3), including reduction in RBC and/or PLT transfusion needs • Overall response (complete remission [CR], partial remission [PR], bone marrow complete response [BMCR], and stable disease [SD] according to 2006 International Working Group (IWG) criteria, including, among responders, the distribution of time to response and the duration of response. (Appendix 3) • Improvements of cytogenetics as evaluated by the change in aneuploidy in BM according to 2006 IWG criteria • Safety and tolerability of tosedostat • Time to AML transformation
Study Design	
This is a single-center, open label, phase II study of clinical activity of tosedostat in adult patients with MDS who have failed prior hypomethylating agent-based therapy. In this study, approximately 80 patients will be enrolled at Weill Cornell Medical College. The dose of tosedostat will be 120 mg once a day continuously for each 28 day treatment cycle. The dose of tosedostat should be taken orally with a glass of water after food preferably in the morning at about the same time every day to ensure an even dose interval.
 
Patients will be assessed for disease response every two cycles as defined in the protocol. If patient has no response as defined by the protocol after two cycles, azacitidine 75 mg/m² SC or IV for 5 days may be combined with tosedostat, at the investigator's discretion.
 
Subjects will be permitted to interrupt tosedostat treatment, to a maximum of 14 days, under circumstances described in Section 6.5. If a subject requires multiple, or prolonged (greater than 14 days) study medication interruptions, the principal investigator will be consulted for a discussion on the subject's continued participation in the study. Investigators are encouraged to avoid unnecessary subject withdrawal. Late response to therapy has been seen in earlier trials, particularly in those who have shown at least stabilization of disease. However, the safety of the subject is paramount and subject's right to withdraw at any time is absolute.

Duration of Clinical Study	Enrollment in this clinical study is expected to be completed in approximately 24 months, and the total study duration, including the 30-day follow up period, will be approximately 36-48 months.
Inclusion Criteria	
 1. Able to understand and to provide written informed consent 2. At least 18 years of age with pathologically confirmed MDS (IPSS-R high or very high) or 20-30% blasts in bone marrow per FAB classification (RAEB-T)

3. Must have received at least 4 cycles of decitabine-based or azacitidine-based therapy and are either refractory to, relapsed after or intolerant to prior therapy with either agent.
 - *Primary failure/refractory:* Stable or worsening disease after a minimum of 4 cycles of decitabine-based or azacitidine-based therapy
 - *Secondary failure/relapse:* Bone marrow blast count increase or loss of hematologic response after initial treatment response with hypomethylating agent-based therapy
 - *Intolerance:* Intolerance of hypomethylating agent-based therapy regardless of number of cycles completed and clinical response
4. Progression (according to 2006 IWG criteria) at any time after initiation of subcutaneous or intravenous azacitidine or decitabine treatment per labeling during the past 2 years, defined as follows:
 - For patients with <5% BMBL, ≥ 50% increase in BMBL to >5% BMBL
 - For patients with 5-10% BMBL, ≥ 50% increase in BMBL to >10% BMBL
 - For patients with 10-20% BMBL, ≥ 50% increase in BMBL to >20% BMBL
 - For patients with 20-30% BMBL, ≥ 50% increase in BMBL to >30% BMBL
 - Any of the following:
 - ≥ 50% decrease from maximum remission/response levels in granulocytes or PLT
 - Decrease in Hgb concentration by ≥2 g/dL
 - Transfusion dependence, defined as administration of at least 4 RBC units in the past 8 weeks before Screening (patients must have Hgb values < 9 g/dL prior to transfusion to be considered), in the absence of another explanation.
5. Has failed to respond to, relapsed following, not eligible, or opted not to participate in BM transplantation
6. Off azacitidine or decitabine for at least 2 weeks, off all other anticancer treatments for at least 2 weeks. Filgrastim (G-CSF) and EPO are allowed before and during the study as clinically indicated
7. Eastern Cooperative Oncology Group (ECOG) performance status of 0-3
8. Subjects must have adequate hepatic and renal function including the following:
 - Total bilirubin ≤ 1.5 x upper limit of normal (in the absence of Gilbert's syndrome)
 - AST and ALT ≤ 2.5 x upper limit of normal
 - Serum creatinine ≤ 1.5 x upper limit of normal
9. Must have acceptable recovery from clinically significant non-hematologic toxicity after prior therapy.
10. Must have a life expectancy of at least 2 months
11. Screening left ventricular ejection fraction (LVEF) > 50% as documented by transthoracic echocardiogram (TTE)
12. Female subjects of child-bearing potential and male subjects with female partners of reproductive potential must use acceptable contraceptive methods (hormonal or barrier method of birth control; abstinence) for the duration of time on study and continue to do so for a further 3 months after the end of tosedostat treatment. Should a female subject become pregnant or suspect she is pregnant while participating in this study, she should inform her treating physician immediately.
13. Able to comply with all study procedures during the study including all visits and tests

	
14. Willing to adhere to the prohibitions and restrictions specified in this protocol
 
15. Patient must sign an informed consent form (ICF) indicating that s/he understands the purpose of and procedures required for the study and is willing to participate.

Exclusion Criteria	
 1. Presence of serious illness, medical condition, or other medical history, involving the heart, kidney, liver, or other organ system, including abnormal laboratory parameters, which, in the opinion of the Investigator, would be likely to interfere with a subject's participation in the study or with the interpretation of the results. 2. Have known active central nervous system disease or active, uncontrolled, clinically significant infection(s) 3. Have other active malignancies or other malignancies within 12 months before enrollment, except non-melanoma skin cancer or cervical intraepithelial neoplasia 4. Are receiving any other investigational therapy or protocol-prohibited therapy 5. Have received previous treatment with tosedostat 6. Pregnant or breastfeeding females 7. Any prior or co-existing medical condition that in the Investigator's judgment will substantially increase the risk associated with the subject's participation in the study 8. Psychiatric disorders or altered mental status precluding understanding of the informed consent process and/or completion of the necessary study procedures 9. Significant* cardiovascular disease defined as: 
 a. Active heart disease including myocardial infarction within 6 months prior to study entry b. Symptomatic coronary artery disease c. Uncontrolled or clinically significant arrhythmia, angina, congestive heart failure d. Presence of clinically significant valvular heart disease e. Presence of clinically significant conduction defect on screening ECG f. Uncontrolled hypertension (i.e., systolic BP >160mmHg, diastolic >90 mmHg in repeated measurements) despite adequate therapy g. Clinically significant atrial fibrillation
	
*Grade 3/4 in the CTCAE v4.0 grading would generally be considered clinically significant, although this remains a judgment for the Investigator to make.
 
 10. LVEF ≤ 50% 11. Baseline troponin I and b-type natriuretic peptide > Grade I 12. Prior exposure cardiotoxic agent, such as anthracycline within 3 months of enrollment 13. Concomitant use of drugs that prolong QT/QTc interval except antibiotics, antifungals, and other antimicrobials used as standard of care for the treatment and prevention of infection and/or other such drugs clinically indicated for patient care. When use of concomitant medications with QT-prolonging potential is necessary, ECG must be repeated 4 hours post-dose on Day 1 (+1 day), on Day 3 (±1 day), and on Day 7 (±1 day), and as clinically indicated, relative to start of agent with QT-prolonging potential. QTc will be calculated using the Fridericia formula. For subsequent use of same concomitant medication, ECG may not be repeated if it did not cause QTc prolongation with tosedostat. 14. Gastrointestinal disorders that may interfere with absorption of drug 15. Active serious infection or sepsis 16. Clinically significant interstitial lung disease
Study duration	24 months
Safety	Safety evaluations will include monitoring of adverse events (AEs); laboratory safety testing,

	including hematology and blood chemistry; urinalysis; physical examinations; vital signs; ECGs; and left ventricular ejection fraction (LVEF) determination. All reported symptoms and AEs will be coded using the Medical Dictionary for Regulatory Activities (MedDRA) and summarized. Crude incidence rates will be based on the maximum intensity grade for each subject. Descriptive statistics for other safety parameters will be produced. All subjects who receive any amount of tosedostat will be included in these analyses.
--	--

Table 1: LIST OF ABBREVIATIONS AND DEFINITIONS OF TERMS

AE	Adverse Event
ALT	Alanine Aminotransferase
AML	Acute Myeloid Leukemia
ANC	Absolute Neutrophil Count
APL	Acute Promyelocytic Leukemia
APTT	Activated Partial Thromboplastin Time
AST	Aspartate Aminotransferase
BP	Blood pressure
BSA	Body Surface Area
BUN	Blood Urea Nitrogen
CFR	Code of Federal Regulations
CFU/c	Colony-Forming Unit in Culture
CML	Chronic Myeloid Leukemia
CPK	Creatinine Phosphokinase
CR	Complete Remission
CPMP	CHMP - Committee for Medicinal Product for Human Use
CRm	Molecular Complete Remission

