1.1.3 Aminopeptidase Inhibition in MDS: Bestatin

Bestatin is another aminopeptidase inhibitor that is utilized in oncology and hematological malignancies. It has antitumor and immunostimulant activity.¹⁶

Bestatin has been widely investigated in the clinic, albeit almost exclusively in Japan. Bestatin is approved in Japan, Korea, and China as a maintenance therapy in patients with non-lymphocytic leukemia after it was shown that it prolonged survival and remission duration, especially in elderly patients. A stimulating effect was also observed on colony forming units in culture (CFU/c). In one study, bestatin, in a daily oral dose of 30 mg, was given for as long as possible even after recurrence of disease and it prolonged overall survival, especially in the elderly Japanese population (50 to 65 years old).

Bestatin has been studied in MDS patients in Japan. In one single-arm study in MDS, 10 out of 13 patients responded after 1 month of oral therapy.¹⁶ In another study of 71MDS patients, overall response was 7%, with median duration of response 10.5 weeks.¹⁷

The clinical activity of bestatin supports aminopeptidase inhibition as a possible therapeutic approach in MDS and supports evaluation of tosedostat in MDS. Tosedostat's pharmacologic activity is improved compared to bestatin in two aspects. First, tosedostat has at least 500-fold greater anti-proliferative activity against AML cell lines than bestatin. Secondly, unlike bestatin, tosedostat is a membrane-permeable ester that is converted inside cells to an active, charged acid. The active metabolite accumulates within the cell and reaches the high

intracellular concentration required to block aminopeptidase activity.¹⁴

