3.1.1 Screening (Study Day -14 to Day 1)

Initiate and complete screening activities within 14 days before Cycle 1, Day 1 treatment, with the exception that informed consent may be obtained within 28 days before Cycle 1, Day 1.

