4.2 EXCLUSION CRITERIA

Subjects meeting any of the following exclusion criteria at Screening will not be enrolled in the

study:

1. Presence of serious illness, medical condition, or other medical history, involving the heart, kidney, liver, or other organ system, including abnormal laboratory parameters, which, in the opinion of the Investigator, would be likely to interfere with a subject's participation in the study or with the interpretation of the results.
2. Have known active central nervous system disease or active, uncontrolled, clinically significant infection(s)
3. Have other active malignancies or other malignancies within 12 months before enrollment, except non-melanoma skin cancer or cervical intraepithelial neoplasia
4. Are receiving any other investigational therapy or protocol-prohibited therapy
5. Have received previous treatment with tosedostat
6. Pregnant or breastfeeding females
7. Any prior or co-existing medical condition that in the Investigator's judgment will substantially increase the risk associated with the subject's participation in the study
8. Psychiatric disorders or altered mental status precluding understanding of the informed consent process and/or completion of the necessary study procedures
9. Significant* cardiovascular disease defined as:
 - a. Active heart disease including myocardial infarction within 6 months prior to study entry
 - b. Symptomatic coronary artery disease
 - c. Uncontrolled or clinically significant arrhythmia, angina, congestive heart failure
 - d. Presence of clinically significant valvular heart disease
 - e. Presence of clinically significant conduction defect on screening ECG
 - f. Uncontrolled hypertension (i.e., systolic BP >160mmHg, diastolic >90 mmHg in repeated measurements) despite adequate therapy
 - g. Clinically significant atrial fibrillation

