5.1 SCREEN PERIOD ASSESSMENT (Study Days -28 to 1)

Initiate and complete all screening activities within 14 days before Day 1 of study. Screening tests may be repeated if minor or transient abnormalities are found in lab values or vital signs. The following assessments will be performed:

- Obtaining and signing informed consent
- Review of inclusion and exclusion criteria
- Recording of subject demographics
- Recording of relevant medical history, to record all relevant past and present medical and surgical conditions, diseases or events including allergies or transplants. Recording should also include prior malignancies (whether primary/secondary MDS and other relevant etiology) and its previous treatment (including chemotherapy regimens and doses)
- Physical examination, including assessment of extramedullary disease
- Recording of ECOG performance status
- Vital signs, including body temperature ($^{\circ}\text{C}$), pulse rate and systolic and diastolic blood

- pressures, height (cm), weight (kg), and body surface area
- Determination of LVEF by echocardiography (ECHO)
- Perform 12-lead ECG
- Collect blood samples for hematology, chemistry, cardiovascular panel (including troponin I, b-type natriuretic peptide), coagulation
- Collect Urinalysis
- Recording of concomitant medications and concomitant significant non-drug therapies, including blood product transfusions
- Bone marrow aspirate and biopsy for assessment of bone marrow morphology, cytogenetics, flow cytometry, and immunophenotyping

Once the patient meets the inclusion and exclusion criteria, a request for registration must be sent. Patients will be registered with the Weill Cornell Medical College (WCMC) Joint Clinical Trials Office (JCTO). To register a patient, email the following documents to the regulatory assistant and regulatory coordinator:

- WCMC Patient registration form
- First and last page of the fully executed informed consent form, plus additional pages if checkboxes for correlative studies are required.
- Fully executed short form, if applicable
- Fully executed HIPAA research authorization form
- Eligibility checklist signed and dated by investigator and research nurse/study coordinator
- Documentation of any eligibility waivers granted
- Source documentation to confirm eligibility
- For inpatients, signed consent documentation template (WCMC only)

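### Pregnancy is an exclusion, but the protocol requires no pregnancy test before the first dose of tosedostat

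*Combined protocol and SAP*

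**What the plan says.** Inclusion criterion 12 (synopsis and section 4.1) lets women of child-bearing potential enrol if they use contraception "for the duration of time on study and continue to do so for a further 3 months after the end of tosedostat treatment". It then relies on self-report: "Should a female subject become pregnant or suspect she is pregnant while participating in this study, she should inform her treating physician immediately". The lower age limit is 18, with no upper limit (inclusion 2).

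Exclusion criterion 6 (synopsis and section 4.2) reads, in full, "Pregnant or breastfeeding females". Section 5.7.4 lists pregnancy among the events that require tosedostat to be stopped.

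For timing, section 3.1.1 says "Initiate and complete screening activities within 14 days before Cycle 1, Day 1 treatment". Only consent may come earlier, up to 28 days ahead. Section 5.2.1.1 allows up to 28 days between the screening visit and Day 1. It also lets Day 1 blood and urine be skipped if they were taken at screening within the previous 7 days.

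Eligibility is checked at screening ("Review of inclusion and exclusion criteria", section 5.1) and again on Cycle 1 Day 1. Registration needs a signed checklist and source documents, and treatment waits for a confirmation email.

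**The concern.** Exclusion 6 concerns whether a woman is pregnant, not whether she knows it. An early pregnancy may be unrecognised, and only a test would show it. If the protocol requires none, a site can complete every listed assessment and still dispense tosedostat to a woman who should not be enrolled.

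Tosedostat is taken every day, and the protocol presents it as an antiproliferative agent. Section 1.1.3 says that "tosedostat has at least 500-fold greater anti-proliferative activity against AML cell lines than bestatin", and the preclinical section reports inhibition of endothelial proliferation and of angiogenesis in vitro. Azacitidine may be added after two cycles (section 6.3). The documents contain no reproductive-toxicity data, and none is assumed here. The exclusion, the contraception rule extending 3 months past treatment and the mandatory stop show that the sponsor already regards fetal exposure as something to prevent.

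**Working it through.** This is a check of text, with a little arithmetic. The plan gives no figure of its own to reproduce.

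**1. Is a test required anywhere before the first dose?** These are the places where a required test would be written down:

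| Place | Entries | Pregnancy tests |
|---|---|---|
| 5.1, screening assessments | 13 | 0 |
| 5.2.1.1, Cycle 1 Day 1 assessments | 13 | 0 |
| 7.3.5, laboratory panels | 5 | 0 |
| Appendix 1, rows | 21 | 0 |

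Total: 13 + 13 + 5 + 21 = 52 entries, 0 pregnancy tests. The 8 footnotes of Appendix 1 add none. The four lists overlap, so 52 records what was read and is not a measure of risk. The urinalysis in 7.3.5 is a dipstick with named analytes, and hCG is not among them.

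**2. Could exclusion 6 be read as covering known pregnancy only?** Exclusion 2 is worded "Have known active central nervous system disease"; exclusion 6 has no such limit. Other test-dependent exclusions do have their test in 5.1: LVEF for item 10, and troponin I and b-type natriuretic peptide for item 11.

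**3. Do the other safeguards amount to a test?**

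- Criteria review at screening and on Day 1 can use only the information available, and no listed procedure produces a pregnancy result.
- The checklist and source documents at registration meet the same limit.
- Contraception does not address conception before it began. Inclusion 12 does not say when time on study starts. If it starts at consent, 0 days between consent and Day 1 are uncovered. If it starts on Day 1, up to 28 are.
- Self-report needs the woman to know or suspect.
- Section 7.3 permits further safety assessments at the investigator's discretion but does not require this one.

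**4. How old could a negative result be at first dose?**

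- Screening test only, under 3.1.1: up to 14 days.
- Screening test only, under the 5.2.1.1 return window: up to 28 days.
- Screening test plus a Day 1 repeat when the result is more than 7 days old: up to 7 days.

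**5. How many patients?** The Introduction puts about 86% of MDS patients over 60 at diagnosis. If this trial matched that, (1 − 0.86) × 80 = 11.2, so about 11 patients would be 60 or younger. If 30% to 50% of those were women (an assumption), that gives 11.2 × 0.30 = 3.4 to 11.2 × 0.50 = 5.6, before removing women past child-bearing. The documents do not allow a firmer number.

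**The case against.** The strongest objection is reach. The disease is mainly one of older people, all patients have already had a hypomethylating agent, and any woman of child-bearing potential must use contraception. The count in step 5 supports this: a handful of women at most, possibly none. That limits how often harm could occur; it does not supply the missing test.

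A second objection is that the protocol leaves other exclusions to history and judgement. Gastrointestinal disorders affecting absorption (item 14) and interstitial lung disease (item 16) are not limited to known disease, and 5.1 lists no dedicated test for either. This is fair, and it weakens the argument from wording and from the tests paired with items 10 and 11. The omission does not depend on that argument, because history and examination cannot reliably exclude an early pregnancy, while a simple test usually can.

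Third, the 28-day figure comes from a return window that conflicts with the 14-day screening rule in 3.1.1 and in the text of 5.1. That is correct: under the stricter rule the figure is 14 days. The case for a repeat near dosing remains.

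Fourth, sites may test anyway. The eligibility checklist and consent pages are not in the documents and might mention a test. The conclusion is therefore confined to what the protocol itself requires. The sections where a required procedure belongs are present and list none.

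**Conclusion.** The concern holds. The protocol excludes pregnant women, admits women who could be pregnant, and requires no pregnancy test before dosing. Confidence is high because the screening list, Day 1 list, laboratory definitions and schedule are all readable and agree.

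This should be corrected. It is a participant-safety gap in a small subgroup whose size the documents do not give. It has no bearing on the sample size, the survival analysis or any other statistical feature. The approximate ceiling of 11 patients aged 60 or younger assumes that the trial's age mix resembles MDS patients generally. The claim does not depend on that figure.

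**What to change.** Add a serum or urine hCG test for women of child-bearing potential to sections 5.1 and 7.3.5 and to Appendix 1, at screening, using blood or urine already being collected. Require a negative result before tosedostat is dispensed on Cycle 1 Day 1. In 5.2.1.1, repeat the test on Day 1 if the screening result is more than 7 days old.

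The repeat follows the existing 7-day laboratory rule. If hCG is taken with the other screening samples, Day 1 blood and urine are already due whenever the repeat is needed. The exception is a patient whose other screening laboratory tests were redone within 7 days but whose hCG was not; she would need a fresh sample for hCG alone. Taking hCG whenever those samples are redone avoids this.

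The cost is amendment wording and one or two inexpensive tests for each eligible woman, with no extra visit. There are two drawbacks: dispensing on Day 1 waits for the result when a repeat is needed, and a very early pregnancy could still be missed.
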